KRANIOPHARYNGEOM Registry 2019 is a prospective, multicenter registry that assesses the prognosis of craniopharyngioma patients in the context of the various currently practiced therapy strategies. Furthermore, long-term prospective follow-up observation of previously recruited patients in HIT-ENDO and KRANIOPHARYNGEOM 2000/2007 is performed as described and anticipated in these previous trials. The KRANIOPHARYNGEOM Registry 2019 is also in line with the perpetuation of reference assessments in the context of the HIT network in order to safeguard the achieved high quality standards.

This registry protocol was compiled with the greatest of care. Nevertheless, errors cannot be completely excluded. It is therefore particularly important to emphasize that each treating physician is solely responsible for any therapy rendered. The registry coordinator accepts no legal responsibility for possible consequences resulting from use of this registry protocol.

Registered brandnames (trademarks) are identified by the ® symbol. However, it should not be concluded that the absence of this symbol means that a brandname is free of restrictions and/or regulations.

This registry protocol is the property of the German Society of Pediatric Oncology and Hematology (GPOH) and copyright protected. It may not be used without permission from the registry coordinator or for purposes other than the execution of the registry.

KRANIOPHARYNGEOM Registry 2019 is most gratefully financially supported by the German Child Cancer Foundation, Bonn (www.kinderkrebsstiftung.de). Certification of KRANIOPHARYNGEOM Registry 2019 by the German Cancer Society (DKG) is in preparation.

According to the joint German federal committee (GBA) resolution of 16 May 2006, a legal directive was passed effective 01 January 2007 stipulating that pediatric patients with oncological diseases are to be treated exclusively in institutional pediatric oncological centers and have to be included in German Society of Pediatric Oncology and Hematology (GPOH) trials. Children and adolescents with craniopharynogioma were specifically included in this legal directive. The out-patient care of children and adolescents with craniopharynogioma during follow-up is not specifically affected by this GBA decision. KRANIOPHARYNGEOM Registry 2019 requests that all colleagues and specialists involved in the follow-up care of craniopharynogioma patients fully participate by registering all patients.

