2.11.1.16. Quality of life (QoL)

Craniopharyngioma and treatment of afflicted children and adolescents means long-term somatic and psychosocial consequences continually affecting their QoL. Additional factors are social reintegration and rehabilitation back into school and occupation, as they impact patients' long-term life planning. Systematic detection of health-related QoL and long-term consequences has not yet been established. Existing reports are on single-center, cross-sectional investigations of small collectives that provide rough estimates regarding somatic and neuropsychiatric long-term consequences based on the QoL conclusions drawn from the respective studies [295]. However, as of yet there is no published report on prospective, multicenter study results (self-rated / parents-rated) for health-related craniopharyngioma patient QoL.

In the HIT-ENDO cross-sectional study, 185 children and adolescents were assessed no less than two yrs after their craniopharyngioma diagnosis by means of questionnaires (KINDL, PedQol, EORTC-QIQ-30) regarding their QoL. The QoL data were evaluated in reference to grade of resection, irradiation, and BMI (BMI SDS). In the calculation, 77 complete datasets were evaluated and compared to age-comparable healthy controls. Craniopharyngioma patients self-rated lower QoL scores with respect to PedQol domains of cognition and social integration in peer groups. Obese patients (BMI>3SD) rated their body image, physical abilities, and social functioning more negatively than the healthy children did. Emotional function was also more negatively self-estimated by craniopharyngioma patients than the healthy children.

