3.3. Work program

3.3.1. Patient recruitment: All patients, which are newly diagnosed with childhood-onset craniopharyngioma (age at diagnosis ≤18 yrs) and registered by specialists involved in their treatment and follow-up care, will be informed about the procedures and aims of the registry. Additionally, patients with xanthogranuloma, cysts of Rathke's pouch, meningioma, pituitary adenoma, and arachnoid cysts will be enrolled in the registry.

The application form for registering patients in the German Childhood Cancer Registry (DKKR) is available in all centers. It is the same form for all tumors and after completion it is to be sent to the German Pediatric Cancer Registry at the Institute for Medical Biometrics, Epidemiology and Medical Informatics, University Hospital Mainz. From there, the primary craniopharyngioma assessment forms will be sent to the recruiting center. Data regarding the frequency and epidemiology of malignant and benign brain tumors is compiled and assessed in collaboration with the DKKR German Pediatric Cancer Registry (Dr. [name], IMBEI at University Mainz).

3.3.2. Interventions: Interventions are not part of the project.

3.3.3. Data acquisition: see CRFs (Appendix section16).

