4.1. Patient recruitment and admission

All patients meeting the inclusion and no exclusion criteria will be enrolled in the KRANIOPHARYN-GEOM Registry 2019.

Inclusion criteria:

- Confirmed histological diagnosis of craniopharyngioma in patients ≤18 yrs by reference pathology
- Informed consent by legal guardians and/or patient to contribute data to the registry

Additionally, Patients with pituitary adenoma or meningioma will be reported by the German Pediatric Cancer Registry (DKKR) to the study coordinator in Oldenburg. Data regarding frequency, diagnostic features, treatment and follow-up in these patients will be collected in context of KRANIOPHARYNGEOM 2019 (see explanation and agreement clarification forms in supplemental information).

Patients with sellar/parasellar cystic deformities (Rathke's pouch cysts, suprasellar cysts, etc.) as well as patients with xanthogranuloma will be reported and tracked by KRANIOPHARYNGEOM 2019. Patient whose imaging indicated a suspected craniopharyngioma, but histological analysis revealed a different diagnosis will be referred, along with their corresponding pathological findings, to the respective GPOH study responsible for these entities.

Exclusion criteria:

- Absence of informed consent by legal guardians and/or patient to contribute data to the registry

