4.2. Statistical endpoints and independent variables

The present protocol is a prospective, multicenter registry with the goal to observe and analyse multidisciplinary treatment approaches in childhood-onset craniopharyngioma. Therefore, several endpoints were chosen that reflect patients' survival and QoL. The association between these endpoints and a set of independent variables that represent diagnostic characteristics and treatment strategies will be analysed. On the basis of previous analyses (e.g., KRANIOPHARYNGEOM 2000 / KRANIOPHARYNGEOM 2007), the independent variables have been divided into two categories according to their expected influence on outcome and prognosis of childhood-onset craniopharyngioma.

Endpoints: - Overall survival (OS) defined as time from diagnosis to death

- Progression-free survival (PFS) defined as time from diagnosis to progression or death (whichever occurs first)
- Quality of life (PedQol, PedsQL, FMH)
- Degree of obesity (BMI SDS)

Factors of influence (mandatory):

- Tumor location (grade of hypothalamic involvement, grade 0-2)
- Neurosurgical treatment strategy (intended radical resection vs.
- incomplete resection + XRT)
- Realized degree of surgical resection (complete resection vs. incomplete resection)
- Postsurgical hypothalamic lesions (grade 0-2)
- Irradiation: modality (photon vs. proton beam therapy) and treatment (dose)

Factors of influence (potential):

- Clinical manifestations and symptoms in history
- Duration of history
- Histology (adamantinomatous vs. papillary type)
- Hydrocephalus at diagnosis
- Patient load of treating neurosurgical units (based on patient load during 10 yrs)
- Patient load of treating radiotherapy units (based on patient load dring 5 or 10 yrs)
- Tumor structure in imaging (tumor volume, cysts, calcifications)
- Endocrine deficiencies (number of deficient hypothalamic-pituitary axes)
- Growth hormone substitution (patient age at initiation, duration)
- Ophthalmological deficits (visual acuity, perimetric deficits)
- Neuropsychological findings, memory deficits, cognition (HIT-Basisdiagnostikum)

- Eating disorders (IEG)
- Experimental therapeutic approaches for obesity treatment (GLP-1R Agonists, Oxytocin)
- Other experimental therapeutic approaches, e.g. intracavitary therapy (intracystic IFN- α)

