4.3. Statistical analysis

The analysis of the data collected in this registry will be mainly descriptive. All inferential analyses will be regarded as exploratory (hypotheses generating) and will be interpreted accordingly. The aim of the analyses is to describe the frequency and modality of treatment approaches and to investigate their influence on survival and QoL. Since the planned study is a purely observational study, no randomized comparisons of treatment strategies are possible. Therefore, in addition to univariable analyses, multivariable analysis strategies are used to take account of different baseline risks due to different demographic or diagnostic characteristics. The model selection in the mutivariable analyses can be done by clinical considerations or by means of automated selection as likelihood-ratio based stepwise selection procedures.

Continuous variables (e.g., BMI SDS, QoL) will be summarised using the following descriptive statistics: n (non-missing sample size), number of missing values, mean, standard deviation, median, Q25%, Q75%, maximum and minimum. Histograms or boxplots will be used for graphical presentation of data. For the comparison of independent groups, statistical tests appropriate to the statistical distribution of the particular endpoint will be used (e.g., Student's t-test, Mann-Whintey U-test). To assess the difference of measurements between two different time points, statistical tests as Student's t-test for paired samples, Wilcoxon signed-rank test, or the sign-test will be applied. For comparison of more than two successive measurements, methods accounting for intra-individual correlation will be used (e.g., Linear Mixed Models), additionally adjusting for potential confounders.

Time-to-event endpoints as OS and PFS will be analysed descriptively using the Kaplan-Meier method. Groups will be compared using the log-rank test. Multivariable analyses will be performed using Cox proportional hazard regression analysis.

For categorical variables, the frequency and percentages (based on the non-missing sample size) of observed levels will be reported. Bar charts will be used for graphical presentation of data. The association of a categorical outcome and categorical independent variables will be analyszed using Fishr's exact test or the χ^2 test.

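### OS and PFS run from diagnosis with no entry-time rule, although patients from earlier studies may come under observation years later; if only those alive at entry are pooled, OS would be overstated

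*Protocol*

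**What the plan says.** **Who is followed.** The introductory notes add the earlier cohorts to the newly registered patients: "long-term prospective follow-up observation of previously recruited patients in HIT-ENDO and KRANIOPHARYNGEOM 2000/2007 is performed". The same notes ask all specialists involved in follow-up care to register all their patients.

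**Who is recruited.** Item 3.3.1 of section 3.3 describes recruitment of "All patients, which are newly diagnosed with childhood-onset craniopharyngioma". The inclusion criteria in section 4.1 are narrower in content and wider in effect. They ask for reference-confirmed histology, age up to 18 years and "Informed consent by legal guardians and/or patient to contribute data to the registry", and none of them requires a new diagnosis. No rule says how earlier-study patients are carried over, or what happens to those who had already died.

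**How time is counted.** Section 4.2 gives "Overall survival (OS) defined as time from diagnosis to death" and "Progression-free survival (PFS) defined as time from diagnosis to progression or death".

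**How it is analysed.** Section 4.3 states: "Time-to-event endpoints as OS and PFS will be analysed descriptively using the Kaplan-Meier method". Groups are compared by log-rank test, and "Multivariable analyses will be performed using Cox proportional hazard regression analysis". Section 4.4 says that missing time-to-event data are treated as right-censored. Delayed entry is not mentioned.

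**What is known of the earlier cohorts.** In HIT-ENDO, a cross-sectional study, "185 children and adolescents were assessed no less than two yrs after their craniopharyngioma diagnosis" (section 2.11.1.16). KRANIOPHARYNGEOM 2000 is described as prospective, with 101 patients.

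**The concern.** A patient first observed some years after diagnosis, and observed only because he or she was alive then, cannot contribute a death to the years before entry. An ordinary Kaplan-Meier curve from diagnosis still keeps that patient in the denominator for those years. The estimated early hazard is diluted and OS is too high. The same faulty risk sets feed the log-rank test and the Cox model, and covariate adjustment does not repair them.

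The risk is clearest for HIT-ENDO, whose assessed patients had already lived at least two years. It could also reach any patient registered from follow-up care long after diagnosis, since section 4.1 would admit such a patient. If late entry were commoner under one treatment strategy than another, the treatment comparisons in section 4.3 would inherit the error.

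**Working it through.** The protocol states no event number, power or precision for OS or PFS, so there is no figure to reproduce. The check asks how large the error could be.

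**Inputs from the protocol**
- OS of 93%, 91% and 87% at 3, 5 and 10 years (section 2.3, patients under 15), used as the true curve.
- 30 new craniopharyngioma patients per year (Synopsis).
- Earlier cohorts: 101 in KRANIOPHARYNGEOM 2000 and 185 assessed in HIT-ENDO; 101 + 185 = 286.

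**Assumptions not in the protocol**
- 5 or 10 years of accrual, with new patients censored uniformly over that period.
- 50, 101, 185 or 286 carried-over patients.
- Entry uniform at 2–12 or 12–18 years after diagnosis, then follow-up for the accrual period.

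**Step 1: hazards** (piecewise exponential, per year)
- 0–3 years: −ln(0.93)/3 = 0.0242
- 3–5 years: −ln(0.91/0.93)/2 = 0.0109
- after 5 years: −ln(0.87/0.91)/5 = 0.0090

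**Step 2: mechanism, one case by hand.** Take 5 years of accrual (150 new patients), 50 carried-over patients, entry at 12–18 years. Before year 3 only new patients can die, but all 50 others are counted at risk. The apparent hazard is the true one times N(t)/(N(t)+50), where N(t) = 150 × (1 − t/5) × exp(−0.0242t).
- t = 0: 150/200 = 0.750
- t = 1.5: 101.3/151.3 = 0.669
- t = 3: 55.8/105.8 = 0.527

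The Simpson average is (0.750 + 4 × 0.669 + 0.527)/6 = 0.659. The apparent cumulative hazard is 0.659 × 0.0726 = 0.0478, so apparent 3-year OS is exp(−0.0478) = 95.3%, against a true 93.0%.

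**Step 3: large-sample simulation.** The earlier patients were treated in three ways: (a) only those alive at entry, counted from diagnosis; (b) the same patients with delayed entry; (c) the whole earlier cohort from diagnosis, early deaths kept. Selected results, OS % at 3/5/10 years:

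| Accrual, carried over, entry | (a) | (b) | (c) |
|---|---|---|---|
| 10 yrs, 50, 2–12 yrs | 94.1/92.3/89.0 | 92.9/90.8/86.8 | 92.9/90.8/86.9 |
| 10 yrs, 101, 2–12 yrs | 94.9/93.5/90.4 | 93.0/91.0/86.9 | 93.0/91.0/87.0 |
| 5 yrs, 50, 12–18 yrs | 95.4/94.7/94.7 | 93.1/91.0/91.0 | 93.0/91.0/86.8 |
| 10 yrs, 286, 12–18 yrs | 96.7/96.0/95.2 | 93.1/91.0/87.1 | 93.1/91.0/87.0 |
| 5 yrs, 286, 2–12 yrs | 98.0/97.5/95.2 | 93.0/91.1/87.1 | 93.0/91.0/87.0 |
| 5 yrs, 286, 12–18 yrs | 98.2/98.0/98.0 | 93.1/91.0/91.0 | 93.0/91.1/87.1 |

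The third row agrees with the hand calculation (95.4% against 95.3%).

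**Step 4: size.** Over all 16 combinations, (a) gives 92.3–98.0% at 5 years (92.3 − 91 = +1.3; 98.0 − 91 = +7.0) and 89.0–98.0% at 10 years (+2.0 to +11.0). The top of the 10-year range comes from 5 years of accrual with entry at 12–18 years. There nobody is truly observed between years 5 and 12, so both curves are flat and 10-year OS is not estimable; the 91.0% under (b) is the 5-year value carried forward. Where year 10 is estimable, the largest value is 95.2%, or +8.2 points. Treatment (c) shows no bias without any special method.

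**The case against.** A reader might infer that the registry follows survivors and that its OS is therefore overstated. The documents do not support that.

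- **Pooling is not stated.** The introductory notes speak of previously recruited patients, and no section places them in the OS/PFS set. Item 3.3.1 describes recruitment of new diagnoses. This stands, and it makes the point conditional.
- **Survivor-only entry is not stated.** The follow-up is presented as foreseen in the earlier studies, which may mean continued observation with early deaths kept. Consent under 4.1 makes entry while alive plausible but does not establish it. KRANIOPHARYNGEOM 2000 was prospective, and KRANIOPHARYNGEOM 2007 randomised the timing of postoperative irradiation, which suggests early enrolment. Complete cohorts of that kind are not truncated. This stands.
- **HIT-ENDO.** The two-year minimum is the timing of a quality-of-life assessment, not a declared start of observation for survival. It shows that late entry is a real prospect, but does not fix anyone's entry date.
- **PFS.** It is tempting to say that PFS is inflated too. Being alive at entry rules out earlier death, not earlier progression, so without knowing how earlier progressions are recorded neither direction nor size follows.
- **Comparison of eras.** Treatment era is not among the factors in 4.2, and comparison with historical cohorts is mentioned only for quality of life. Distortion of an era comparison is possible, not planned.
- **Left to an analysis plan, and exploratory.** Kaplan-Meier and Cox from diagnosis are compatible with left truncation, and a plan not shown may add it. But the protocol itself fixes origin, estimators and right-censoring while bringing in patients for whom these may not suffice. An exploratory label does not remove bias.

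**Conclusion.** The point holds in conditional form. As written, the time-to-event methods have no provision for patients who come under observation late, while the introductory notes and the section 4.1 criteria leave room for such patients.

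If patients alive at carry-over were pooled and counted at risk from diagnosis, OS would be too high by about 1 to 7 points at 5 years and 2 to 11 points at 10 years (2 to 8 where year 10 is estimable). For scale, section 2.3 reports a 5-year difference of 8 points between the 1980s and 1990s (88% against 96%).

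These sizes rest on the section 2.3 survival figures as the true curve and on assumed accrual, cohort sizes and entry times. The error is zero if the earlier cohorts enter complete from diagnosis or stay out of the OS/PFS set. For PFS no size or direction is claimed.

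**What to change.** In sections 4.1 and 4.3:

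1. State whether patients from HIT-ENDO and KRANIOPHARYNGEOM 2000/2007, and others registered well after diagnosis, belong to the OS/PFS analysis set.
2. If they do, keep diagnosis as time origin but let each patient join the risk set only at the date prospective observation began, in Kaplan-Meier, log-rank and Cox alike. For patients enrolled prospectively near diagnosis in an earlier study, with early events retained, that is the earlier enrolment date.
3. For PFS, say how progressions before entry are recorded and handled.
4. If they do not belong to the set, report them separately.

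The analysis change is small: one entry-date variable and an entry-time option in the survival procedure. Results are unchanged if nobody enters late. The costs are smaller early risk sets, possibly with stretches of follow-up where OS cannot be estimated, and the need for an entry date in the data. The case report forms are not shown, so whether that date is already collected must be checked.

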The multicenter **KRANIOPHARYNGEOM 2000** surveillance study prospectively evaluated referenceconfirmed data of 101 pediatric craniopharyngioma patients regarding their neuroradiological diagnostics, therapy and prognosis (QoL and functional capacity). Therapeutical recommendations and randomization were not included in the scope of KRANIOPHARYNGEOM 2000. The results of KRANIOPHARYNGEOM 2000 were as follows:

- Hypothalamus involvement in a craniopharyngioma tumor represents the most important risk factor for impaired long-term prognosis (QoL and functional capacity).
- The most significant increase in body mass index (BMI) resulting in long-term severe hypothalamic obesity occurs during the first 12 month after diagnosis/surgery.
- A radical excision is not recommended in cases of hypothalamus involvement with consideration of severe sequelae due to gross total resection.

KRANIOPHARYNGEOM 2007 analyzed by means of a randomized investigation, the optimal timing of postoperative irradiation (XRT) (immediate postoperative XRT vs. XRT in response to progression) in craniopharyngioma patients ≥ 5-year (yr). The primary endpoint of KRANIOPHARYNGEOM 2007 was patient QoL assessment measured by PedQoI.

The duration of the study was subdivided into a phase running up until the interim analysis (IA), and the recruitment phase following IA – running up until the end analysis (EA). In 2016, the IA was carried out after recruitment of 20 randomized patients and an observation of over three yrs. The IA phase yielded little therapy-effecting results. Accordingly, the randomization was stopped in 2016.

KRANIOPHARYNGEOM Registry 2019 will prospectively collect and descriptively analyse data on diagnostics, treatment, and follow-up of patients with craniopharyngioma. In continuation of preceding studies also patients with xanthogranuloma, meningioma, pituitary adenpma, prolactinoma and cystic intracranial malformations will be registered.

The registry is open for collaborative projects and investigations.

KRANIOPHARYNGEOM Registry 2019 – Synopsis

- **Title:** KRANIOPHARYNGEOM Registry 2019 Multicenter registry for patients with childhoodonset craniopharyngioma, xanthogranuloma, cysts of Rathke's pouch, meningioma, pituitary adenoma, arachnoid cysts
- Short Title: KRANIOPHARYNGEOM Registry 2019
- Investigator: PD Dr. med. [name], Universitätsklinik für Kinder- und Jugendmedizin, Klinikum Oldenburg AöR, Oldenburg
- **Topic:** Childhood-onset craniopharyngioma, xanthogranuloma, cysts of Rathke's pouch, meningioma, pituitary adenoma, arachnoid cysts
- Objectives: Collect epidemiological information
 - Collect information on treatment and outcome to determine whether a relationship exists between outcomes and specific interventions
 - Collect information on late effects and QoL
 - Assess the quality of treatment by the means of data collection, data check and an advisory service provided by the registry and the reference centers
 - Establishment of a tumor bank as a base for further biological studies to define new molecular risk factors and to identify new targets for therapy

Expected case numbers:

- 30 craniopharyngioma patients/yr
- 10 patients with other sellar masses/yr
- Endpoints: Overall survival (OS)
 - Progression-free survival (PFS)
 - Quality of life (PedQol, PedsQL, FMH)
 - Degree of obesity (BMI SDS)

Factors of influence (mandatory):

- Tumor location (grade of hypothalamic involvement, grade 0-2)
- Neurosurgical treatment strategy (intended radical resection vs. incomplete resection + XRT)
- Realized degree of surgical resection (complete resection vs. incomplete resection)
- Postsurgical hypothalamic lesions (grade 0-2)
- Irradiation: modality (photon vs. proton beam therapy) and treatment (dose)

Factors of influence (potential):

- Clinical manifestations and symptoms in history
- Duration of history
- Histology (adamantinomatous vs. papillary type)
- Hydrocephalus at diagnosis
- Patient load of treating neurosurgical units (based on patient load during 10 yrs)
- Tumor structure in imaging (total volume, cysts, calcifications)
- Endocrine deficiencies (number of deficient hypothalamic-pituitary axes)
- Growth hormone substitution (patient age at initiation, duration)
- Ophthalmological deficits (visual acuity, perimetric deficits)
- Neuropsychological findings, memory deficits, cognition (HIT-Basisdiagnostikum)
- Eating disorders (IEG)
- Experimental therapeutic approaches for obesity treatment
- (GLP-1R Agonists, Oxytocin)
- Other therapeutic approaches, i.e. intracavitary therapy (intracystic interferone α (INF- α))

Inclusion criteria:

Confirmed histological diagnosis of craniopharyngioma, xanthogranuloma, cysts of Rathke's pouch, meningioma, pituitary adenoma or arachnoid cysts in patients ≤18 yrs by reference pathology.

Informed consent by legal guardians and/or patient to contribute data to the registry.

Exclusion criteria:

Absence of informed consent by legal guardians and/or patient to contribute data to the registry.

Statistical methods:

The aim of the statistical analyses is to describe the frequency and modality of treatment approaches as well as diagnostic features and to investigate their influence on survival and QoL. The association between endpoints reflecting survival and QoL and a set of independent variables that represent diagnostic characteristics and treatment strategies will be analyzed. Descriptive and inferential methods appropriate to the distribution of the particular endpoint will be chosen (e.g. Kaplan-Meier estimator, log-rank test, Student's t-test, Mann-Whitney U-test). Since the planned study is observational, multivariable analysis strategies as Cox regression, linear regression or (linear) mixed model analyses are primarily used in addition to univariable analyses to enable adjusted analyses. All inferential analyses will be regarded as exploratory (hypotheses generating) and will be interpreted accordingly.

Ethical considerations:

The registry will be conducted in accordance with the Declaration of Helsinki, the current revision of ICH, and the local law.

KRANIOPHARYNGEOM Registry 2019 – Synopse

- **Titel:** KRANIOPHARYNGEOM Registry 2019 Multizentrisches Register für Kinder und Jugendliche mir Kraniopharyngeom, Xanthogranulom, Zysten der Rathkeschen Tasche, Meningeom, Hypophysenadenom, Arachnoidalzysten
- Kurztitel: KRANIOPHARYNGEOM Registry 2019
- Koordinator: PD Dr. med. [name] Universitätsklinik für Kinder- und Jugendmedizin, Klinikum Oldenburg AöR, Oldenburg
- **Thema:** Kraniopharyngeom, Xanthogranulom, Zysten der Rathkeschen Tasche, Meningeom, Hypophysenadenom, Arachnoidalzysten im Kindes- und Jugendalter

Ziele:

- Sammlung epidemiologischer Daten
 - Sammlung von Informationen zu Behandlung und Behandlungsergebnis sowie retrospektive Auswertung des Zusammenhangs zwischen Intervention und Ergebnis
 - Erfassung von Spätfolgen und Lebensqualität
 - Beurteilung der Qualität der Behandlung durch Datensammlung, Datenüberprüfung und Beratung durch das Registerzentrum und die Referenzeinrichtungen
 - Schaffung einer Tumorbank als Grundlage für zukünftige biologische Forschungsvorhaben zur Identifizierung neuer Risikofaktoren und Angriffspunkte für zielgerichtete Therapeutika

Erwartete Fallzahlen:

30 Kraniopharyngeompatienten/Jahr

10 Patienten mit anderer sellären Raumforderungen/Jahr

- Endpunkte: Gesamtüberleben
 - Ereignisfreies Überleben
 - Lebensqualität (PedQol, PedsQL, FMH)
 - Grad der Adipositas (BMI SDS)

Einflussfaktoren (mandatory):

- Tumorlokalisation (Grad der Hypothalamus-Beteiligung, Grad 0-2)
- Neurochirurgische Strategie (intendierte radikale Resektion vs. inkomplette Resektion + XRT)
- Realisierter Grad der Resektion (komplette Resektion vs. inkomplette Resektion)
- Postoperative hypothalamische Läsionen (Grad 0-2)
- Strahlentherapie: Modalität (Photonen- vs. Protonenbestrahlung) und Behandlungsplanung (Dosis)

Einflussfaktoren (potentiell):

- Symptome in der Vorgeschichte
- Anamnesedauer
- Histologie (adamantinomatöser vs. papillärer Typ)
- Hydrocephalus bei Diagnosestellung
- Zentrumsgröße (basierend auf der Anzahl rekrutierter Patienten während 10 Jahren)
- Tumorstruktur in der Bildgebung (Tumorvolumen, Zysten, Verkalkungen)
- Endokrine Ausfälle (Anzahl der defizienten hypothalamisch-hypophysären Achsen)
- Wachstumshormonsubstitution (Alter bei Therapiebeginn, Therapiedauer)
- Opthalmologische Defizite (Visual acuity, Gesichtsfeldausfälle)
- Neuropsychologische Befunde, Gedächtnis, Kognition (HIT-Basisdiagnostikum)
- Störungen des Essverhaltens (IEG)
- Experimentelle Therapieansätze zur Adipositasbehandlung und Prävention (GLP-1R Agonisten, Oxytocin)
- Andere Therapieansätze wie z.B. intracavitäre Therapie (intrazystisches IFN- α)

Einschlusskriterien:

Referenzpathologisch bestätigte histologische Diagnose eines Kraniopharyngeoms, eines Xanthogranuloms, Zysten der Rathkeschen Tasche, eines Meningeoms, eines Hypophysenadenoms oder Arachnoidalzysten im Kindes- und Jugendalter (Alter bei Diagnose ≤ 18 Jahre).

Zustimmung (Informed consent) der gesetzlichen Vertreter und/oder des betroffenen Patienten zur Teilnahme am Register.

Ausschlusskriterien:

Fehlende oder widerrufene Zustimmung (Informed consent) der gesetzlichen Vertreter und/oder des betroffenen Patienten zur Teilnahme am Register.

Statistische Methoden:

Ziel der statistischen Analysen ist es, Häufigkeit und Modalität verschiedener Behandlungsansätzen sowie diagnostischer Kriterien zu beschreiben und ihren Einfluss auf das Überleben und die Lebensqualität zu untersuchen. Der Zusammenhang zwischen Endpunkten, die das Überleben und die Lebensqualität widerspiegeln, und einer Reihe von unabhängigen Variablen, die diagnostische Merkmale und Behandlungsstrategien darstellen, wird analysiert. Entsprechend der Verteilung des jeweiligen Endpunktes werden geeignete deskriptive und inferenzstatistische Methoden verwendet (z.B. Kaplan-Meier-Schätzer, Log-Rank-Test, Student's t-Test, Mann-Whitney U-Test). Da es sich um eine reine Beobachtungsstudie handelt, werden neben univariablen Analysen vorrangig multivariable Analysestrategien wie z.B. Cox-Regression, lineare Regression oder (lineare) gemischte Modelle eingesetzt, um adjustierte Analysen zu ermöglichen. Alle Analysen werden als explorativ (d.h. hypothesengenerierend) erachtet und entsprechend interpretiert.

Ethikrichtlinien:

Das vorliegende Register wird gemäß der geltenden gesetzlichen Bestimmungen und Richtlinien sowie der aktuellen Richtlinie der International Conference on Harmonisation of Technical Requirements for Registration of Pharmaceuticals for Human Use (ICH-Richtlinie) für GCP (Good Clinical Practice) durchgeführt. Die Richtlinien der Deklaration von Helsinki werden eingehalten.

Table of contents

1. Introduction	. 14
2. Background	. 15
2.1. Embryology	. 15
2.2. Pathology and molecular biology	. 15
2.3. Epidemiology	. 16
2.4. Anatomical localization	. 16
2.5. Clinical symptoms	. 16
2.7. Natural course of disease	. 18
